1.3 SCHEDULE OF ACTIVITIES (SoA)

Procedures	Screening	Intervention	Conclusion
Informed Consent	X		
Demographics	X		
Inclusion/ Exclusion	X		
Administer Study Intervention		X	
Surveys	X	X	X
Photos	X		X
Adverse Event Review and Evaluation	X	X	X

2 INTRODUCTION

2.1 STUDY RATIONALE

The effects of aging and poor skincare on the face, neck, and chest can be significant, leading to various visible changes in skin appearance and texture. As we age, our skin naturally produces less collagen and elastin, proteins that provide structural support and elasticity¹. This reduction, combined with environmental factors like sun exposure and pollution, contributes to the development of wrinkles, fine lines, and sagging skin^{2,3}.

The decolletage area, which includes the neck and upper chest, is particularly vulnerable to aging signs due to its thin skin and frequent sun exposure⁴. Common symptoms in this region include vertical wrinkles, crepey skin, sun spots, and overall skin discoloration. The face often experiences similar issues, along with the formation of age spots, rough patches, and a loss of volume that can lead to a sunken appearance⁵.

Poor skincare habits exacerbate these natural aging processes. Neglecting sun protection, failing to moisturize regularly, and not incorporating anti-aging ingredients into one's routine can accelerate skin damage⁶.

Light therapy devices have emerged as a promising treatment for aging skin. These devices use specific wavelengths of light to stimulate collagen production, improve skin texture, and reduce the appearance of fine lines and wrinkles⁷. LED (Light Emitting Diode) therapy, in particular, has

shown benefits in skin rejuvenation⁸. Red light therapy can boost collagen production and improve skin elasticity, while blue light therapy may help with acne and inflammation^{9,10}.

With this in mind, Freedom Laser Therapy has designed a face mask and neck and chest mask that utilize 360 LEDs for the face mask and 230 LEDs for the neck & chest mask to provide firmer, smoother, and clearer skin.

2.2 RISK/BENEFIT ASSESSMENT

Immediate risks: People taking or using medications that make their skin photosensitive should not take part in this study.

Long-term risks: There are no expected long-term risks associated with this product.

Immediate benefits: Participants may experience plumped skin, smoothed fine lines and wrinkles, reduced pigmentation, improved skin tone and texture, calmed skin, reduced redness, firmer skin and elasticity, improved skin radiance, and reduction of crepey skin on neck and chest.

Long-term benefits: Participants may experience improvements in overall mental health and well-being due to the immediate benefits of the product.

3 OBJECTIVES AND ENDPOINTS

OBJECTIVES	ENDPOINTS	TIMEPOINTS	ASSESSED BY	JUSTIFICATION FOR ENDPOINTS
Primary Objective : To evaluate changes in overall skin appearance, as measured by dermatologist skin grading.	Improvement in Skin Appearance	Baseline and Week 12	Photographs via Dermatologist Skin Grading	Standardized photographs provide objective data on the changes in skin appearance, specifically targeting wrinkles, fine lines, and other signs of aging.

Secondary Objectives: To assess changes in a range of skin health parameters.	Improvement in skin plumpness, fine lines and wrinkles, pigmentation, tone and texture, redness, firmness, elasticity, radiance, and appearance of crepey skin.	Baseline, Week 2, Week 4, Week 6, Week 8, Week 12	Questionnaires	Self-reported questionnaires provide subjective data on perceived changes in wrinkles and fine lines.
--	---	---	----------------	---

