6.3 RANDOMIZATION AND BLINDING

There will be no randomization or blinding in this trial.

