6.5 PHOTO INSTRUCTIONS

Photographs will be taken at Baseline and Week 12 to document changes in appearance.

Face guidelines:

- You will be required to provide photos taken straight on, directly facing the camera, and from the sides at each measurement time point.
- Hair should be tied back.
- The photo should include your full face/head only, with no more than the top of your shoulders visible.
- No cropping: your full face, head, and ears should be included.
- Please use natural light, in a direction that your phone does not cast a shadow on your face when taking the photo, without using the flash.
- Do not use any type of camera filter setting. No makeup should be worn. Neutral facial expression.
- If possible, take your photos in the same location, at the same time of day, and in the same lighting at each check-in.

Neck and Chest Guidelines:

- The photo should be taken straight ahead.
- Please use natural light, in a direction that your phone does not cast a shadow on your face when taking the photo, without using the flash.
- Do not use any type of filter setting. No makeup should be worn. Neutral facial expression.
- If possible, take your photos in the same location, at the same time of day, and in the same lighting at each check-in.

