6.6 REQUIRED DEVICES

Smartphone or digital camera to be provided by participants. iRESTORE Illumina LED Face Mask and The iRESTORE Illumina LED Neck & Chest Mask will be provided by the sponsor.

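### Section 3 rests the sole primary endpoint on standardized photographs, but Section 6.5 makes matching of the Baseline and Week 12 photos optional and sets no same-camera rule

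*Combined protocol and SAP*

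**What the plan says.** The primary endpoint is dermatologist grading of photographs taken at Baseline and Week 12 (Sections 1.1 and 3). The justification column in Section 3 reads "Standardized photographs provide objective data on the changes in skin appearance"; the row below it describes questionnaires as giving subjective data.

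Section 6.5 has one guide for the face and one for the neck and chest. Many of its rules carry no qualifier:

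- Both guides: "Please use natural light, in a direction that your phone does not cast a shadow on your face", with no flash. The neck and chest guide adds "Do not use any type of filter setting. No makeup should be worn. Neutral facial expression", and the face guide has equivalent rules.
- View: front and sides for the face; for the neck and chest, "The photo should be taken straight ahead".
- Face only: hair tied back, no cropping, and "The photo should include your full face/head only, with no more than the top of your shoulders visible".

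Matching between the two time points is qualified. Both guides say "If possible, take your photos in the same location, at the same time of day, and in the same lighting at each check-in". On equipment, Section 6.6 says "Smartphone or digital camera to be provided by participants", and the devices row of the Section 1.1 synopsis agrees. Nothing asks for the same camera at both time points.

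Section 6.3 states "There will be no randomization or blinding in this trial", and Section 7 plans comparisons with Baseline by repeated-measures tests that it does not name. Section 8.4 mentions internal quality checks in the data system, with automatic range checks as the only example.

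**The concern.** The endpoint is the difference between two photographs of the same person taken 12 weeks apart. Rules on makeup, filters and expression improve each photograph. What makes the pair comparable is that camera, place, hour and light are the same both times, and those are the conditions left optional or unmentioned. The signs to be graded, such as fine lines and wrinkles, are read from the image, so a change in light or camera can look like a change in skin.

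Two consequences follow. Differences in photographic conditions that vary from one participant to another add variance to the change score and cost power. A difference common to participants, for example a seasonal change in natural light, would enter the mean change directly. With no concurrent control group, it could not be separated from an effect of the devices.

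**Working it through.** **Text comparison.** For each capture condition, what the plan fixes:

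| Condition | Face | Neck and chest |
|---|---|---|
| View | fixed | fixed |
| Natural light, no phone shadow, no flash | fixed | fixed |
| No filter, no makeup, neutral expression | fixed | fixed |
| Framing, hair tied back | fixed | not stated |
| Same location, time of day, lighting | only if possible | only if possible |
| Same camera at both time points | not stated | not stated |
| Photo check at upload | not described | not described |

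The type of light is fixed. Its intensity and colour, and the matching of both between time points, are not. On the last row, the checks in Section 8.4 do not establish that anyone looks at the photographs. The Manual of Procedures named in Section 8.5 might describe such a review but is not among these documents.

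**Illustration of the noise.** Section 5.4 gives no power, effect size or standard deviation, so there is no plan figure to reproduce. Only N = 38 comes from the plan. Assumed inputs: 38 complete pairs, a paired t-test, two-sided 5%, a share f = 20% of pairs that do not match, and extra variance v of 50% or 100% in each of those pairs. SD means the standard deviation of change in a matched pair.

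1. Starting point. With df = 37 the critical t is 2.026. The noncentral t distribution gives 80% power at 0.467 SD (noncentrality 0.467 × √38 = 2.88).
2. Average variance when all pairs are graded is 1 + f × v: 1 + 0.2 × 0.5 = 1.10, or 1 + 0.2 × 1.0 = 1.20.
3. Effect detectable at 80% power: 0.467 × √1.10 = 0.489 (up to rounding), or 0.467 × √1.20 = 0.511 SD.
4. Power for the 0.467 SD effect: noncentrality 2.88/√1.10 = 2.74 gives 76%; 2.88/√1.20 = 2.63 gives 72%.

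**Should non-matching pairs be discarded?** Discarding 20% of 38 (7.6, so 8) leaves 30 pairs. With df = 29 the critical t is 2.045 and the detectable effect is 0.529 SD, worse than the 0.489 to 0.511 from grading all. In general, the variance of the mean is proportional to (1 + f × v)/n if all are kept and to 1/[n(1 − f)] if non-matching pairs are dropped. Keeping all is better while v < 1/(1 − f), which at f = 0.2 is v < 1.25. This comparison concerns variance only and assumes that mismatch does not shift the mean.

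**The case against.** The best defence is that Section 6.5 is a serious capture protocol: most conditions are set without qualification. That stands. A reader might infer from the optional matching line that the photographs are not standardized at all, and the documents do not support that.

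The word *objective* also has a fair reading. Beside the questionnaire row it plausibly separates grading by an assessor from self-report and makes no claim of laboratory imaging. That stands too, so the contrast can be kept in clearer words.

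It can be said that the remote design is deliberate, as Section 4.2 explains, and that participants must use their own cameras. This is true but does not answer the point, because asking for the same phone in the same place needs no clinic visit.

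Finally, an instruction to match, with leave to send non-matching photographs, is close to the current line. The real additions are the same-camera rule, the record of departures and the analysis that uses it. Natural light will still vary with weather and season. The matched-pair analysis will not reveal a seasonal shift that affects matched pairs as well.

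**Conclusion.** The mismatch between Section 3 and Sections 6.5 and 6.6 is real and should be corrected, although the study can run without the change. The photographs are partly standardized, and the gap lies in the matching of the two time points.

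The size is not known. The fall from 80% to about 76% to 72% rests on an assumed test, mismatch share and variance, and only shows scale. Two stronger readings should be resisted:

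- A reader might apply extra variance of 25% to 100% to the average of all 38 pairs and quote power of 71% down to 51%. Nothing in the documents supports inflation of that size across the whole group.
- A reader might infer a particular false-positive rate, or that the primary result must be biased towards benefit. A common shift would be inseparable from a device effect, but the documents give neither its size nor its direction.

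The point concerns photo capture only. The grading scale and masking of the grader are separate questions. So is whether neck and chest photographs are graded: Section 1.1 mentions faces, whereas Section 1.2 lists all three areas, and the two need reconciling.

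**What to change.** 1. **Section 6.5, both guides.** Replace the optional matching line with: *Use the same camera, location, time of day and lighting set-up at Baseline and Week 12. If you cannot, still send the photos and record what differed.* A recorded departure then follows the instruction and is not in itself a deviation under Section 8.5.
2. **Section 7.** State that all photographs are graded and kept in the main analysis, that non-matching pairs are flagged, and that a sensitivity analysis uses matched pairs only.
3. **Section 3.** Replace the reference to standardized photographs with: *Participant-taken photographs under a standard instruction, graded by a dermatologist*. Matching reduces natural-light differences but does not remove them. The contrast with the questionnaires can be kept as assessor-graded versus self-reported.

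The cost is three text edits, one extra question at upload, a slight burden on participants and one extra analysis. Remote capture and the visit schedule do not change, and no photograph is lost from the primary analysis. The wording needs to be in place before Baseline photographs are taken, because a Baseline photograph cannot be repeated once device use has begun.

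Optional, and not needed for the point: a check of Baseline photographs by the CRO before first device use.

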4 STUDY DESIGN

4.1 OVERALL DESIGN

This 12-week single-group, virtual clinical study is designed to evaluate the efficacy of the iRESTORE Illumina LED Face Mask and The iRESTORE Illumina LED Neck & Chest Mask. The study will involve 38 participants, aged between 25 and 55 years, with self-reported skin issues, who will use the devices once daily for 10 minutes daily for 12 weeks.

Data collection will include questionnaires at Baseline, Week 2, Week 4, Week 6, Week 8, Week 10, and Week 12. In addition, participants will provide photos at Baseline and Week 12 to assess changes in skin health and appearance.

4.2 SCIENTIFIC RATIONALE FOR STUDY DESIGN

A single-group study is an appropriate design to understand the efficacy and safety of the test product. A design that encompasses 12 weeks is also long enough to determine if the supplement is effective at improving skin health. The data collection intervals for this trial were chosen to minimize the burden on the patients (i.e., not having to travel to a clinic) while still collecting valuable data about the efficacy of the test product over time.

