1 PROTOCOL SUMMARY

1.1 SYNOPSIS

Title:	The Effects of an LED Face Mask & Neck and Chest Mask On Skin Health
Study Type:	Single Group, Virtual
Product(s) being tested	The iRESTORE Illumina LED Face Mask and The iRESTORE Illumina LED Neck & Chest Mask
Study Intervention Description:	
This single-group study will involve 38 participants for a total of 12 weeks.
 
Participants will use the test products once daily for 10 minutes in the evening while getting ready for bed.
 
Participants will use Mode 1 only for all sessions of the face mask - the neck and chest mask does not have multiple settings.
 
Participants will complete questionnaires at Baseline, Week 2, Week 4, Week 6, Week 8, Week 10, and Week 12.
 
Participants will also provide photos of their faces at Baseline and Week 12 for dermatologist skin grading.
 
Participants will utilize the test products at home and complete questionnaires online.

Objectives:	
Primary Objective: To examine the effectiveness of the iRESTORE Illumina LED Face Mask and The iRESTORE Illumina LED Neck & Chest Mask in improving skin health outcomes.
 
Secondary Objective: To assess changes in participant perception of skin health.

Endpoints:	
Primary Endpoint: Improvements in skin health parameters will be evaluated by dermatologist grading at Baseline and Week 12.
 
Secondary Endpoint: Participant perceptions of skin health, including plumpness, fine lines and wrinkles, appearance of pigmentation, skin tone and texture, skin redness, firmness, and radiance, and the appearance of crepey skin will be evaluated through subject-specific questionnaires at Baseline, Week 2, Week 4, Week 6, Week 8, Week 10, and Week 12.

Study population	38 female participants aged 25-55
Study Duration:	12 weeks
Description of Sites/Facilities Enrolling Participants:	Virtual

Survey Milestones	Baseline, Week 2, Week 4, Week 6, Week 8, Week 10, and Week 12.
Photo Milestones	Baseline and Week 12

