7 STATISTICAL CONSIDERATIONS

Following data collection and the completion of the trial, the data will be analyzed by Citruslabs to determine the effect of the intervention. Repeated-measure, between time points, statistical tests will be used to examine changes in primary and secondary endpoints versus the Baseline.

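### Sections 4.2 and 7 claim efficacy and an intervention effect that an uncontrolled, unblinded contrast with Baseline cannot establish; separately, the 5.2 cosmetic-treatment exclusion is limited to facial treatments although neck and chest are also treated

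*Combined protocol and SAP*

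**What the plan says.** **Claims about what the study can show.** Section 4.2 states that "A single-group study is an appropriate design to understand the efficacy and safety of the test product" and that 12 weeks is "long enough to determine if the supplement is effective at improving skin health". Section 7 gives the purpose of the analysis as "to determine the effect of the intervention".

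**Aims in the same vein.** The Synopsis primary objective begins "To examine the effectiveness of the iRESTORE Illumina LED Face Mask", and Section 4.1 says the study "is designed to evaluate the efficacy of the iRESTORE Illumina LED Face Mask". Section 3 is more restrained: its primary objective is to evaluate changes in overall skin appearance by dermatologist grading.

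**What the design and analysis provide.** Section 7 plans tests to "examine changes in primary and secondary endpoints versus the Baseline". Section 6.3 states: "There will be no randomization or blinding in this trial". No control group, external comparator or performance threshold appears. Adverse event review is scheduled in Section 1.3, but Section 3 has no safety endpoint and Section 7 plans no adverse event summary.

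**Cosmetic-treatment exclusion.** Section 5.2 excludes women who plan facial treatments (botox, filler and peels are the examples) or had them in the last 3 months. The neck and chest are treated too (1.2, 6.1) and photographed (1.2, 6.5). Crepey skin, which Section 5.1 places on the neck and chest, is a secondary endpoint.

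**The concern.** With one group and a before-after test, the observed mean change is the sum of any device effect and everything else that moves the ratings over 12 weeks. That includes expectation in unblinded participants, regression to the mean in women enrolled because of self-reported skin concerns, and differences in photo conditions. On the last, Section 6.5 asks for the same location, time of day and lighting only where possible. The planned test has no way to separate these parts. If Sections 4.2 and 7 stand, a significant change from Baseline could be reported as the effect of the masks on the protocol's own authority.

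The safety half of the 4.2 sentence has data collection behind it but no planned summary.

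The eligibility issue is separate and smaller. A recent cosmetic treatment of the neck or chest could alter the Baseline or the later course of the crepey-skin ratings, and Section 5.2 does not clearly bar it as it does for the face.

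**Working it through.** **1. Is there a plan figure to reproduce?** No. Section 5.4 justifies 38 participants without alpha, power, effect size, SD or dropout, and Section 7 names no specific test. What follows is an illustration under assumptions.

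**2. Behaviour of a Baseline-only test when the device does nothing.** Assumptions: paired t-test, two-sided alpha 0.05, and a true non-device mean shift of d, in units of the SD of change. The values of d are assumed. The n of 38 is from Section 5.4. The n of 34 and 30 are assumed numbers of completers, shown because Section 6.4 does not replace participants who withdraw after receiving the intervention.

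Chance of significant improvement = P(T > t(0.975, n−1)), where T is noncentral t with n−1 degrees of freedom and noncentrality d√n. For n=38, √38 = 6.164 and the critical value is 2.026. The noncentralities are 0.1 × 6.164 = 0.616, 0.2 × 6.164 = 1.233 and 0.3 × 6.164 = 1.849.

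| n | d = 0 | d = 0.1 | d = 0.2 | d = 0.3 |
|---|---|---|---|---|
| 38 | 2.5% | 8.7% | 22.4% | 43.7% |
| 34 | 2.5% | 8.2% | 20.4% | 39.7% |
| 30 | 2.5% | 7.6% | 18.4% | 35.5% |

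The smallest observed mean change that reaches p<0.05 is t(0.975, n−1)/√n. This is 2.026/6.164 = 0.329 SD of change at n=38, 2.035/5.831 = 0.349 at n=34 and 2.045/5.477 = 0.373 at n=30. The test answers whether the mean changed; it does not address why.

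**3. What a safety summary could show at n=38.** Exact (Clopper-Pearson) two-sided 95% intervals for the proportion with an event:

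- 0 participants: 0 to 9.3% (upper limit 1 − 0.025^(1/38) = 0.093)
- 1 participant: 0.1 to 13.8%
- 2 participants: 0.6 to 17.7%

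**4. Which neck and chest treatments does Section 5.2 leave open?** The criteria side by side:

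| Criterion | Body area | Window |
|---|---|---|
| Cosmetic treatments | face only, as worded | prior 3 months, or planned |
| Invasive medical procedure | any | prior three weeks |
| Planned procedure | any | during the study |
| Surgical procedure | neck | upcoming |

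Planned procedures and very recent invasive ones are therefore already covered in whole or part. What remains is mainly past treatment of the neck or chest: non-invasive within the prior 3 months, or invasive between 3 weeks and 3 months before. For the face, the same kinds of treatment are barred over the full 3 months.

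**The case against.** The strongest reply is that the single-group design is fully disclosed and was chosen. That stands: a reader might infer that the design itself is the error, but it suits the Section 3 objective of evaluating changes. It is also fair that the Synopsis and Section 4.1 state aims and draw no conclusion. The claims about what the design can deliver are in 4.2 and 7, and the other two places need changing only for consistency.

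A reader might also infer that nothing in the plan guards against other causes of change. The documents do not support that. Section 5.1 requires a skincare routine stable for one month and kept unchanged, skin-directed supplements stable for 3 months, and no new skin-targeting products, prescriptions or supplements. Section 6.4 calls for withdrawal if a new drug or antibiotics are started. Section 6.5 sets natural light, no flash, no filter and no makeup without qualification. These rules narrow the list of alternatives but do not replace a control, and they do not address expectation or regression to the mean.

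The shifts of 0.1 to 0.3 SD are generic. They would apply to any uncontrolled study of this size, and unmatched lighting may add noise rather than a shift towards improvement. This objection stands, so the percentages are not an estimate of error in this trial. Masking the grader to photo time point would be possible without a control and would remove one source of bias, but it would still leave the change without a comparator.

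On Section 5.2, a reader might infer that neck and chest procedures are unrestricted, or that the primary endpoint is compromised. Neither follows. Planned procedures are barred, and the Synopsis has participants "provide photos of their faces at Baseline and Week 12 for dermatologist skin grading", with no mention of grading neck or chest photos. A reader might also see a bias in the sun-avoidance and sunscreen criteria of Section 5.1; the documents show no effect from these, and they form no part of this point.

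**Conclusion.** The concern holds in a limited form. Sections 4.2 and 7 state a property that the design lacks: a Baseline-only contrast without control or blinding cannot by itself attribute change to the masks. The protocol already has wording it can support, in Section 3. This conclusion rests on the text alone. The 9% to 44% range at n=38 shows only how the test would behave under an assumed non-device shift, an assumed paired t-test and an assumed alpha.

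The safety wording in 4.2 lacks a planned summary. Even with no events in 38 participants, an incidence of up to 9.3% would remain compatible with the data.

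The restriction to facial treatments in Section 5.2 is a real mismatch with the treated and photographed areas, with a narrow remaining gap. Its bearing is most direct on the crepey-skin ratings and uncertain for the primary endpoint. The documents give no basis for estimating how many participants it would affect or by how much. Both parts should be fixed; neither prevents the study from being run.

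**What to change.** 1. In Sections 4.2 and 7, and for consistency in the Synopsis primary objective and Section 4.1, state that the study estimates change from Baseline during use of both masks and does not by itself establish device efficacy.
2. Support the safety wording in 4.2 by adding to Section 7 the incidence of adverse events with an exact confidence interval, from the review already scheduled in Section 1.3. Otherwise remove the safety wording.
3. Reconcile Section 5.2 with the treated and photographed areas, so that the existing cosmetic-treatment exclusion covers face, neck and chest.

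Cost: a less favourable claim, a short adverse event table, a reworded screening item and possibly a few more screen failures, whose number cannot be estimated from the documents. No participants or visits are added.
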